### **Data Quality**

All data will be examined for completeness and an assessment of missing data will be performed to check for any biases which may occur. Data will be monitored and entered promptly in order to detect issues as they arise. Special attention will be paid to note what, if any, demographic and clinical factors may be related to subject attrition, retention and adherence. Study retention refers to those who complete all study-related assessments. Dose-effects will be accounted for based on the number of treatment sessions attended by each subject relative to their assigned group. Analyses will be performed to determine what if any covariates may be predictive of missing data over time and these variables will be adjusted for in subsequent models. Close attention will be paid to underlying normality assumptions. Numerical transformations (such as square root, log, and inverse functions) may be applied to correct for deviations due to skewness.

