### **Power Analysis**

Given the estimated final sample size of 104 (52 per group) after expected levels of attrition (50% attrition from 210), we will be powered at 80% to detect moderate effect sizes for any differences between the groups (two-group independent t-tests effect size (Cohen's d) of 0.555 and chi-square tests for differences in proportions between the two-groups effect size (Cohen's omega,  $\omega$ ) 0.274 and higher) as well as moderate-to-large effect sizes detected for differences between the groups over time (repeated measures group-by-time interaction effects: effect size of 0.28, Cohen's f) will be detected. Power analyses will be completed using PASS v.13.0.8.

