## Statistical Analysis Post hoc: Equivalence Testing

### Detailed Methods:

While the original RCT was designed for inequality hypothesis testing, given the lack of differences seen between the 2 treatments (both performed well), we additionally conducted equivalence tests of means between the two treatment groups using two one-sided unequal-variance t-tests (TOST). These equivalence tests were performed using the TOSTER v.0.4.0 package for R [REFS Lakens (2017); Lakens, Scheel and Isager (2018)]. The changes from baseline to each follow-up time point were computed for each participant. These change scores were then used to perform two one-sided t-tests (TOST) between the two treatment groups to test for equivalence and reject the presence of the smallest effect size of interest (SESOI). This approach essentially checks to see if the 90% confidence interval bounds for the mean difference between the two groups are within the limits defined by the SESOI. Similar to Sloan, et.al. (2022), a margin of 10 was used as the SESOI. Sloan was only interested in one-side of the margin and performed non-inferiority tests since they assumed one treatment might be inferior to the other. However, we did not have an initial assumption that one treatment would be better than the other, so two one-sided tests or TOSTs were performed to test for equivalence within +/- 10 points. This SESOI was used for both the CAPS-5 and PCL-5 change score differences between the two treatment groups. It has also been suggested that a difference as small as 5 points for the CAPS-5 may be useful for comparing treatments for PTSD so the mean and standard deviation of all changes scores are also reported by group and time for descriptive comparisons. For clinical diagnostic comparisons, similar to Schnurr, et.al. (2022), the percentage of participants at each time point who still have PTSD are reported as well as the percentage who achieved a clinical response (reduction of CAPS-5 severity scores by 10 or more points from baseline), loss of diagnosis (CAPS-5 change  $\leq -10$ , no PTSD diagnosis and CAPS-5 severity score  $< 25$ ), as well as those who achieved remission (loss of diagnosis plus CAPS-5 score  $< 12$ ). All statistical analyses completed using SPSS version 27.0.0.0 [IBM Corp (2020)] and R version 4.1.2 [R Core Team (2021)].

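### The post hoc equivalence test takes no account of sessions attended, so it supports equivalence of the arms as assigned but not, by itself, equivalence of the two treatments as received

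*Combined protocol and SAP*

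**What the plan says.** The section on post hoc equivalence testing (Detailed Methods) explains that the trial was designed to look for a difference and that equivalence was examined after none was seen. On who enters the test it says: "The changes from baseline to each follow-up time point were computed for each participant". It continues: "These change scores were then used to perform two one-sided t-tests (TOST) between the two treatment groups to test for equivalence". The comparison is made "using two one-sided unequal-variance t-tests (TOST", with no covariate, and "TOSTs were performed to test for equivalence within +/- 10 points" for both CAPS-5 and PCL-5. The decision rule "checks to see if the 90% confidence interval bounds for the mean difference between the two groups are within the limits" set by the margin. No minimum number of sessions, per-protocol set or attendance sensitivity analysis is mentioned.

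Elsewhere the plan treats attendance as relevant. Section E, Data Quality, says that dose-effects will be allowed for using the "number of treatment sessions attended by each subject relative to their assigned group". It names no model, cut-off or analysis set, and the post hoc section does not take the idea up. The same paragraph defines retention by completed assessments, not by sessions. The intervention descriptions give ten sessions for yoga and twelve for CPT.

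Section E, Power Analysis, gives an "estimated final sample size of 104 (52 per group") "after expected levels of attrition (50% attrition from 210"). It gives no sample size or power for an equivalence test and no attendance figures.

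**The concern.** A woman who came to one or two sessions but gave follow-up scores counts in the equivalence test exactly as a woman who completed treatment does. In a test for difference, non-receipt that dilutes the contrast makes a false positive less likely. In an equivalence test the same dilution makes it easier to pass. The move from one question to the other therefore reversed the direction of this risk, and the post hoc section adds nothing to show how large it might be.

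What is at stake is the reach of the conclusion. A pass in all women with a change score is evidence that being assigned to yoga or to CPT leads to similar mean change. Readers choosing between treatments will want to know whether the two are similar for women who actually receive them, and this test alone does not answer that.

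**Working it through.** **The plan's own figure.** With 52 per group, d = 0.555 and two-sided alpha 0.05 (assumed; not stated), the noncentral t gives 80.0% power, as the plan states. That figure concerns the original difference test only.

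**Inputs.**
- From the documents: 52 per arm, margin 10, 90% confidence interval, unequal-variance t-test.
- Assumed, because the documents do not give them: SD of change 12 (varied below); a true difference of 10 points, exactly on the margin, among adequately treated women; a share p of adequately treated women, equal in both arms; and a difference r among the rest, set to 0 or 5.

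**Formulas.**
- Difference between arms as assigned: D = 10p + r(1 − p).
- Mixing two kinds of women widens the variance in one arm by (10 − r)² × p(1 − p).
- SE = √[(144 + 144 + (10 − r)² p(1 − p)) / 52].
- Equivalence is declared when the observed difference is below 10 − 1.66 × SE. The lower bound hardly matters here.
- Chance of passing ≈ Φ[(10 − 1.66 × SE − D) / SE].

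**Example, p = 0.5 and r = 0.** D = 5. SE = √[(288 + 25)/52] = 2.453. The threshold is 10 − 4.07 = 5.93. Φ(0.93/2.453) = Φ(0.38) = 65%.

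**Results at SD 12, by simulation of the unequal-variance test** (the formula agrees to within about one percentage point):

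| Adequately treated | D if r = 0 | Pass, r = 0 | D if r = 5 | Pass, r = 5 |
|---|---|---|---|---|
| 100% | 10 | 5% | 10 | 5% |
| 80% | 8 | 20–21% | 9 | 11% |
| 70% | 7 | 34% | 8.5 | 15% |
| 50% | 5 | 65% | 7.5 | 27% |

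**Other SDs, r = 0, at 80/70/50% treated.**
- SD 10: 25/42/77%
- SD 15: 16/26/50%
- SD 20: 12/18/33%

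**What an attended-only test does.** In this model the difference among attenders stays at 10, so the chance of passing returns to about 5%. The price is power. With a true difference of 0 and SD 15, the chance of passing is 92% with 52 per arm, 53% with 26 and 3% with 10.

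**The case against.** The strongest reply is that the test is not wrong for the question it asks. In the scenarios with r = 0, the arms as assigned really differ by 8, 7 or 5 points, all inside the margin, so a pass is correct for assignment. The aims concern effectiveness relative to CPT, for which the comparison as assigned is a legitimate target. This stands. A reader might infer that the method produces a false equivalence finding; that holds only if the result is read as a statement about the treatments as received.

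Two further inferences are tempting and not supported:
- The 50% attrition might be taken as a sign of poor attendance. It is the loss that takes 210 to 104. Retention is defined by assessments, and a woman with no follow-up score cannot dilute the test. If poor attenders are mostly lost to follow-up, dilution is smaller and the issue becomes one of missing data.
- The remark that both treatments did well might be taken as a conclusion drawn from passing. In the text it is part of the reason for running the test.

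The size is also conditional. The larger figures assume no difference at all among the under-treated, equal shares in both arms and a true difference on the margin. Partial attenders still receive different treatments, and with r = 5 the figures fall by roughly half or more. Unequal attendance could move the difference in either direction.

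Finally, the plan does not ignore attendance, since Data Quality mentions dose. What remains is that this general sentence names no analysis and is not applied to the equivalence test, which has no covariate and no attendance-based set.

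**Conclusion.** The point holds in a limited form. The equivalence test in all women with a change score supports equivalence of assignment to the two treatments. Without a companion analysis by sessions received, it does not by itself support equivalence of the treatments when received.

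Under the assumptions stated (SD 12, 52 per arm, a true difference of 10 among the adequately treated), a pass occurs in about 20%, 34% and 65% of trials with 80%, 70% and 50% treated if the others do not differ. If the others differ by 5 points, it occurs in about 11%, 15% and 27%. These figures show that the gap can matter. They do not estimate its size in this trial, because the SD, the treated share and the true difference are not in the documents. Nothing there shows that attendance was in fact low.

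**What to change.** In the post hoc equivalence section:

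1. Report the distribution of sessions attended, by arm, among the women who enter the equivalence test at each time point.
2. Add the same test, with estimate and 90% confidence interval, as a labelled sensitivity analysis among women who attended a stated share of their own arm's sessions. A share is needed because the arms offer ten and twelve sessions. Name and justify one main cut-off; show any others descriptively.
3. Word the conclusion as equivalence of assignment to the two treatments. Extend it to the treatments as received only if the estimate and interval in the attended set are consistent with that.

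The work is small, since Data Quality already relies on the number of sessions each woman attended. The downside is real: the attended set is smaller, is not protected by randomisation, and would be defined after results are known. It should therefore inform the wording of the conclusion and not serve as a pass/fail gate. As the power figures above show, a strict cut-off could block a true claim through small numbers alone.
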